Safety and Efficacy of Trim II for Non- invasive Lipolysis and Circumference Reduction of Abdomen

NCT05398159

Last Updated Jun 3 2022

I N M O D E

Safety and Efficacy of Trim II for Non-invasive Lipolysis and Circumference Reduction of Abdomen.

Protocol No: DO609924A SIRB ID: 8659

Rev. Date: Jun 3 2022

Study Name: Safety and Efficacy of Trim II for Non-invasive Lipolysis and Circumference Reduction of Abdomen.

Protocol No.: DO609924A

Sponsor: InMode Ltd.
[name]
[name]
[name]
[contact]

I N M O D E

Safety and Efficacy of Trim II for Non-invasive Lipolysis and Circumference Reduction of Abdomen.

[figure not shown]
Protocol No: DO609924A SIRB ID: 8659

Rev. Date: Jun 3 2022

Approvals:

Revision Log:

Revision #	Date	Modification
A	January 2021	First Release
B	June 2022	

I N M O D E

Safety and Efficacy of Trim II for Non-invasive Lipolysis and Circumference Reduction of Abdomen.

Protocol No: DO609924A SIRB ID: 8659

Rev. Date: Jun 3 2022

1. Protocol Synopsis

Study Title	Safety and Efficacy of Trim II for Non-invasive Lipolysis and Circumference Reduction of Abdomen.
Protocol No	DO609924A
Sponsor	InMode Ltd.
Investigational Product	Trim II hands free device.
Study Design	Prospective, open label clinical study.
Principle Investigator and Study Site	Site 01: Site 02: Site 03: Site 04: Site 05:
Patient Population and Sample Size	At least 70 female and male subjects, from 5 investigational sites, aged 18-70 seeking non-invasive lipolysis and circumference reduction of abdomen will be enrolled.
Study Duration	Eligible subjects will receive 3 bi-weekly treatments (once in 2 weeks) with Trim II hands-free applicator belt according to the study protocol. Trim II hands-free applicator composed of 4 units applied to the abdominal area, using a single-use belt. Each treatment duration will be 45-60 minutes. Study duration for each subject is approximately 6 months (including screening, 3 treatments and 2 follow-up visits at 1 and 3 months post last treatment). Histological samples will be taken from treated area of 8-10 subjects (in total) at baseline and at 3 months follow-up visit. Overall study duration will be approximately 12 months, depending on the subject recruitment rate.

I N M O D E

Safety and Efficacy of Trim II for Non-invasive Lipolysis and Circumference Reduction of Abdomen.

Protocol No: DO609924A SIRB ID: 8659

Rev. Date: Jun 3 2022

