6.1 Primary Endpoints

- Efficacy of the Trim II treatment for lipolysis and abdominal circumference reduction.
Evaluation of change in abdomen circumference using tape measurements in cm at the 3 months follow-up visit comparing to baseline.
Success criteria: Statistically significant reduction in abdominal circumference tape measurements at the 3 months follow-up visit compared to baseline.
* The primary effectiveness endpoint will be calculated based on those patients whose weight remains stable during the study period. A subject is defined as having maintained her weight during the treatment period if it remained within $\pm 3\%$ (inclusive) of baseline for the respective period.

 I N M O D E	Safety and Efficacy of Trim II for Non-invasive Lipolysis and Circumference Reduction of Abdomen.	
	Protocol No: DO609924A SIRB ID: 8659	Rev. Date: Jun 3 2022

- Safety of the Trim II treatment for lipolysis and abdominal circumference reduction. The occurrence of adverse events will be followed throughout the whole study. Observation, assessment and recording of potential reactions by the investigator. Evaluations will be done immediately after each treatment and at the follow-up visits. The frequency, severity and causality of reactions will be recorded.

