6.2 Secondary Endpoints

- Efficacy of the Trim II treatment for fat and circumference reduction in abdomen, as assessed by two blinded evaluators. Evaluation of photographs at baseline and 3 months follow-up. Success criteria: Correct identification of baseline and 3-month follow-up visit photographs in at least 70% of treated subjects by two blinded evaluators.
- Change in abdominal fat thickness measured by ultrasound imaging (USI) at the 3 months follow-up visit comparing to baseline. Success criteria: statistically significant change in fat thickness measurements at the 3 months follow-up visit compared to baseline.
- Evaluation of change in histological samples at 3 months follow-up visit comparing to baseline. Success Criteria: Effect on fat tissue with no adverse effect in dermal tissue
- Subject's satisfaction with study treatment at 3 months follow-up visit. Subject's satisfaction with the therapy results evaluated through the Subject Satisfaction Questionnaire (5-point scale) as follows: +2 = Very satisfied; +1 = Satisfied; 0 = Indifferent; -1 = Disappointed; -2 = Very disappointed.
- Therapy comfort during the study treatment. Subjects will be asked to classify skin reactions (subjective evaluation) and will rate discomfort using visual analog pain scale from 0 (no pain) to 10 (intolerable pain) immediately after each treatment session.

7. Study Population

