14.1 Analysis Sets

- Safety Analysis Set

The safety analysis set will include all subjects using Embrace procedures at least a single time.

- Performance Analysis Set

Performance analysis set will consist of all subjects providing at least one post treatment performance measurement.

- Treatment of Missing Values

Only observed data will be used; i.e. missing data will not be imputed.

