14.2 Statistical Analysis

[figure not shown]
Means, and standard deviations for each characteristic will be calculated. Paired sample t-test will be computed to assess changes in before treatment and follow-up scores. Statistical significance will be calculated and two-tail significance level of 0.05 will be used.

15. Data Management Plan

Case Report Forms and questionnaires will be retrieved by Monitors after source data verification and resolution of monitoring queries. Documents will be delivered to InMode Ltd onsite data management facility where forms will be logged in, and then data will be entered using a double entry method.

16. References

4. [name], [name] Neuromascular Electrical Stimulation and Strength Recovery

I N M O D E

Safety and Efficacy of Trim II for Non-invasive Lipolysis and Circumference Reduction of Abdomen.

Protocol No: DO609924A SIRB ID: 8659

Rev. Date: Jun 3 2022

of Postnatal Diastasis Recti Abdominis Muscles. Ann Rehabil Med 2017;41(3):465-474 pISSN: 2234-0645 • eISSN: 2234-0653

17. Investigator Study Acknowledgment

Investigator’s Statement:

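### Weight stability protects only the tape endpoint: weight loss counts as device effect on ultrasound and photographs, and within ±3% the tape result is only partly protected

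*Combined protocol and SAP*

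**What the plan says.** The synopsis describes the design as "Prospective, open label clinical study" and the population as "At least 70 female and male subjects, from 5 investigational sites, aged 18-70". Every subject is treated and is compared with his or her own baseline.

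- **Primary, tape (section 6.1).** Success is a statistically significant reduction at 3 months, with no minimum in centimetres. A note adds: "The primary effectiveness endpoint will be calculated based on those patients whose weight remains stable during the study period". The tolerance is ±3% of baseline, inclusive, in either direction.
- **Secondary, ultrasound (section 6.2).** "Success criteria: statistically significant change in fat thickness measurements at the 3 months follow-up visit compared to baseline". No weight condition is attached.
- **Secondary, photographs (section 6.2).** "Correct identification of baseline and 3-month follow-up visit photographs in at least 70% of treated subjects by two blinded evaluators". The denominator is treated subjects, again with no weight condition.
- **Analysis set (section 14.1).** "Performance analysis set will consist of all subjects providing at least one post treatment performance measurement". Weight plays no part.
- **Test (section 14.2).** "Paired sample t-test will be computed to assess changes in before treatment and follow-up scores", and a "two-tail significance level of 0.05 will be used". No covariate is named.

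Section 8.5 and Appendix 1.0 have weight recorded at baseline, before the second and third treatments and at both follow-up visits.

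**The concern.** By restricting the tape analysis, the plan accepts that body weight can move the result for reasons other than the device. Subcutaneous fat thickness and before/after appearance are open to the same influence, yet they carry no such protection. A subject who loses 8% of body weight drops out of the tape result but stays in the ultrasound and photograph results, where the loss helps both criteria.

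Ultrasound matters most here. It is the only quantitative measure of fat among the endpoints that support the lipolysis objective; caliper readings are taken but are not an endpoint. Without a control arm, nothing else in the analysis separates weight loss from device effect.

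For tape there is a residual question: how much weight loss does the tolerance let through, and could that amount meet a criterion that asks only for significance?

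**Working it through.** **Inputs from the documents.** n = 70 (minimum); two-sided alpha 0.05; paired t-test; tolerance ±3%; photograph threshold 70%. The documents give no SD of change, effect size, power, expected weight drift or centimetres per kilogram. The sample size therefore cannot be reproduced, and everything marked *assumed* below is a range.

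**Step 1. Smallest significant mean tape reduction.** Formula: t(0.975, n−1) × SD / √n. SD of change 2, 3, 4 cm *assumed*.

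| n | SD 2 | SD 3 | SD 4 |
|---|---|---|---|
| 70 | 0.48 cm | 0.72 cm | 0.95 cm |
| 50 | 0.57 cm | 0.85 cm | 1.14 cm |

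**Step 2. What a 3% loss does to girth.** *Assumed*: fixed height and circumference proportional to the square root of weight. The fall is C × (1 − √0.97), which is 1.21, 1.36 and 1.51 cm for C = 80, 90 and 100 cm.

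**Step 3. Mean loss that reaches significance.** At C = 90 cm and n = 70, the loss is 1 − (1 − threshold/90)². This gives 1.06%, 1.58% and 2.11% for SD 2, 3 and 4 cm, all inside the tolerance. A different *assumed* scaling, 0.5–1.0 cm per kg at 70–80 kg, gives 0.6–2.7%.

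**Step 4. What the cut does to that mean.** The ±3% rule removes the larger losers, so a cohort mean is not a retained mean. With normal weight change and SD 2% (*assumed*):

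| Retained mean loss | Cohort mean loss needed | Retained of 70 |
|---|---|---|
| 1.06% | about 2.1% | about 47 |
| 1.58% | about 3.5% | about 28 |
| 2.11% | about 5.9% | about 5 |

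The upper part of the range in step 3 is therefore hard to reach with 70 retained subjects unless they lose similar percentages. Section 7.2 allows replacement to reach 70 completers, not 70 weight-stable subjects.

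**Step 5. Simulated false success with zero device effect.** *Assumed*: 70 subjects, weight-change SD 2%, 0.45–0.70 cm per 1% of weight, residual SD 1.5–3.5 cm; 4,000 trials per scenario.

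| Cohort mean weight change | Paired t-test, ±3% set | Paired t-test, all subjects |
|---|---|---|
| 0 | near 2.5% | near 2.5% |
| −1% | 7–34% | 17–81% |
| −2% | 13–79% | 53–100% |

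The last column shows what an unrestricted paired test does in this tape model. It is only an analogy for ultrasound, because the documents do not say how fat thickness responds to weight.

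**Step 6. Same scenarios, tested at zero weight change.** Regress each subject's change on percent weight change and test the intercept. False success was about 2–3% in every scenario, both in the ±3% set and in all subjects. The simulated relation is linear, which favours this test.

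**Step 7. Photographs.** 0.70 × 70 = 49 correct identifications are needed. The binomial probability of 49 or more is 0.05% at pure guessing, 56% if the true identification rate is 70%, and 98% if it is 80%. The criterion responds to visible change whatever its cause.

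**The case against.** A reader might infer that the ±3% tolerance is wide enough to deliver tape success on its own. The documents do not support that. The tolerance is symmetric, and false success stays at the nominal level unless retained subjects lose weight on average. The rule also gives real protection: at a 1% cohort mean loss it brings false success from 17–81% down to 7–34%.

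A reader might also infer that these subjects are likely to lose weight. No section gives any weight drift. Subjects seek circumference reduction, which makes a lean towards loss plausible, but that remains an assumption. The visible text contains no condition on diet, exercise or weight-loss drugs. Parts of the document are redacted or removed, so this cannot be read as proof that none exists. Section 7.4 does exclude other abdominal treatments during the study, and Appendix 1.0 records concomitant medication at every visit.

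Three further objections have force. The unprotected endpoints are secondary, and primary success does not depend on them. The tape calculation takes ±3% to bound weight at the 3-month visit, whereas section 6.1 refers to both the study period and the treatment period, and the synopsis omits the weight rule. Finally, weight change is measured after baseline, so adjusting for it relies on a roughly linear relation and on weight change not being an effect of the device.

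None of this answers the central point: section 6.2 lacks the condition that section 6.1 treats as necessary.

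**Conclusion.** The point holds on the text for ultrasound and photographs. The plan treats weight as a confounder for tape and leaves it uncontrolled for both of these criteria.

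For tape it holds as a conditional possibility. A retained mean loss of about 1.1–2.1% would be enough at n = 70, girth 90 cm, SD 2–4 cm and square-root scaling. False success is about 7–79% for a cohort mean loss of 1–2% under the assumptions of step 5, and near 2.5% if there is no net weight change. Every one of these inputs beyond n, alpha and the tolerance is assumed.

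This is a change the sponsor should make. It does not show that the primary analysis fails.

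**What to change.** 1. **Photographs (6.2).** Judge the 70% criterion in the weight-stable set, defined by weight at the 3-month visit, and report all treated subjects alongside.
2. **Ultrasound (6.2, 14.2).** Name one deciding analysis: the mean change at zero weight change, that is, the intercept from regressing change on percent weight change at the 3-month visit. Report the paired results in the weight-stable set and in all subjects as supportive.
3. **Tape (6.1, 14.2).** Keep the paired t-test in the ±3% set. Report the same weight-adjusted intercept beside it, and claim a device effect only if that also shows a reduction.

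**Cost.** No new data are needed, but the protocol change needs IRB approval under section 10.3. With no mean weight change, about 61 of 70 subjects stay within ±3% if the weight-change SD is 2%, and about 48 if it is 3% (assumed). The intercept is less precise when mean loss is large. For a true 1 cm effect, mean loss 2% (SD 2%), 0.45 cm per 1% and residual SD 3.5 cm, simulated power in the ±3% set is about 33%, against about 80% for the paired test. Part of that 80% is weight loss rather than device effect. With no weight drift, power is about equal or slightly better. Adjustment does not replace a control arm.

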6.2 Secondary Endpoints

- Efficacy of the Trim II treatment for fat and circumference reduction in abdomen, as assessed by two blinded evaluators. Evaluation of photographs at baseline and 3 months follow-up. Success criteria: Correct identification of baseline and 3-month follow-up visit photographs in at least 70% of treated subjects by two blinded evaluators.
- Change in abdominal fat thickness measured by ultrasound imaging (USI) at the 3 months follow-up visit comparing to baseline. Success criteria: statistically significant change in fat thickness measurements at the 3 months follow-up visit compared to baseline.
- Evaluation of change in histological samples at 3 months follow-up visit comparing to baseline. Success Criteria: Effect on fat tissue with no adverse effect in dermal tissue
- Subject's satisfaction with study treatment at 3 months follow-up visit. Subject's satisfaction with the therapy results evaluated through the Subject Satisfaction Questionnaire (5-point scale) as follows: +2 = Very satisfied; +1 = Satisfied; 0 = Indifferent; -1 = Disappointed; -2 = Very disappointed.
- Therapy comfort during the study treatment. Subjects will be asked to classify skin reactions (subjective evaluation) and will rate discomfort using visual analog pain scale from 0 (no pain) to 10 (intolerable pain) immediately after each treatment session.

7. Study Population

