- RF - Radiofrequency
- IPL – Intense Pulsed Light
- EMS - Electrical Muscle Stimulation

I N M O D E

Safety and Efficacy of Trim II for Non-invasive Lipolysis and Circumference Reduction of Abdomen.

Protocol No: DO609924A SIRB ID: 8659

Rev. Date: Jun 3 2022

NMES - Neuromuscular Electrical Stimulation

USI – Ultrasound Imaging

AE - Adverse Events

SAEs - Serious Adverse Events

UADEs - Unanticipated Adverse Device Effects

ICF – Informed Consent Form

CRF- Case Report Form

[figure not shown]
4. Device Description

The Trim II applicator is a hands-free medical aesthetic device applying combined bi-polar RF energy and muscle activation.

[figure not shown]
The non-invasive bi-polar RF treatment is targeting the dermal and subdermal tissues. The EMS repeatedly contracts muscles by passing electrical currents through electrodes contacting the treated body area.

[Redacted text]

[Redacted text]

[Redacted text]

I N M O D E

Safety and Efficacy of Trim II for Non-invasive Lipolysis and Circumference Reduction of Abdomen.

Protocol No: DO609924A SIRB ID: 8659

Rev. Date: Jun 3 2022

[REDACTED]

The System provides individual adjustment of RF and EMS intensity level to achieve maximum efficacy, safety and comfort for each patient. The System provides enhanced safety while minimizing possible side effects by constantly monitoring RF parameters.

Another safety feature is a hand-held switch (Figure 2) that interrupts the treatment process and switches the system to pause state until the operator re-enables it. The patient can use the hand-held switch to pause the treatment if the discomfort becomes excessive.

5. Study Objectives

The Primary Objective of this trial is to evaluate the safety and efficacy of the Trim II treatment for lipolysis and abdominal circumference reduction.

6. Study Endpoints

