7.2 Subject Withdrawal and Replacement

Subjects enrolled in the study can discontinue their participation at any time for any reason without prejudice or reduction in the quality of their medical care. The investigators or sponsor can terminate a

	Safety and Efficacy of Trim II for Non-invasive Lipolysis and Circumference Reduction of Abdomen.	
	Protocol No: DO609924A SIRB ID: 8659	Rev. Date: Jun 3 2022

subject's participation in this study to protect the subject's health or if the subject fails to follow directions resulting in noncompliance to study procedures. Subjects who withdraw or are terminated from the study may be replaced to ensure that at least 70 subjects have completed the study. Subjects who fail to complete the treatment will be replaced and will not be evaluable.

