- Baseline circumference tape measurement. Appendix 4.0
- Baseline caliper measurement
- Baseline histologies (8 subjects – at selected sites).

Treatment:

- 1st abdominal treatment will be done using the TRIM II hands-free applicators belt according to IFU
- Subject Comfort Assessment
- * Treatment may occur on the same day of screening or within 3 weeks following screening.
- If the Screening and Treatment procedures are not conducted on the same day, the urine pregnancy test will be repeated on the first treatment day.

Treatment procedure:

- Treatment will be conducted according to instructions in the operator manual and company guidelines.

I N M O D E

Safety and Efficacy of Trim II for Non-invasive Lipolysis and Circumference Reduction of Abdomen.

Protocol No: DO609924A SIRB ID: 8659

Rev. Date: Jun 3 2022

[Redacted text block]

After treatment:

- Observation, assessment and recording of adverse events will be conducted.
- Subject will complete Therapy Comfort Questionnaire

8.2 Visits 2-3: 2nd , 3rd treatments , every 2 weeks following previous visit

- Pregnancy Urine Test prior to the treatment
- Weight and height (BMI calculation)
- Circumference tape measurement
- Caliper measurement
- Abdominal treatment will be done using the TRIM II hands-free applicators belt according to IFU

	Safety and Efficacy of Trim II for Non-invasive Lipolysis and Circumference Reduction of Abdomen.	
	Protocol No: DO609924A SIRB ID: 8659	Rev. Date: Jun 3 2022

- Therapy Comfort Questionnaire

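### Sections 7.2 and 14.1 conflict on whether comfort scores already collected from subjects who stop treatment are analysed, and satisfaction describes only those who return at 3 months

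*Combined protocol and SAP*

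**What the plan says.** **Comfort.** Under section 6.2 subjects "will rate discomfort using visual analog pain scale from 0 (no pain) to 10 (intolerable pain) immediately after each treatment session". Section 8.1 places the first assessment straight after treatment 1: "Subject will complete Therapy Comfort Questionnaire". Table 1 (section 8.5) and Appendix 1.0 repeat it after every treatment, which gives up to three scores per subject.

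**Satisfaction.** Section 6.2 defines it as "Subject's satisfaction with study treatment at 3 months follow-up visit". Table 1 and Appendix 1.0 schedule it at that visit only. No questionnaire at early exit is described.

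**Who counts.** Section 7.2 says: "Subjects who withdraw or are terminated from the study may be replaced to ensure that at least 70 subjects have completed the study". It then adds: "Subjects who fail to complete the treatment will be replaced and will not be evaluable". Section 14.1 defines a different population: "Performance analysis set will consist of all subjects providing at least one post treatment performance measurement". On missing values the same section says: "Only observed data will be used; i.e. missing data will not be imputed".

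Section 6.2 sets no success criterion for comfort or satisfaction. The paired t-test in section 14.2 does not fit either of them, because neither has a pre-treatment score. What remains is a descriptive summary.

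**The concern.** Comfort is an endpoint for which the reason for stopping may be the outcome itself. The plan allows that discomfort can become marked: section 4 says of the device that "The patient can use the hand-held switch to pause the treatment if the discomfort becomes excessive", and pain is on the list of anticipated adverse effects in section 9.2. If some subjects stop because a session hurt, their scores are among the high ones, and those scores were collected before they left. An analyst who follows 7.2 would delete them. An analyst who follows 14.1 might keep them. The protocol does not choose between the two, so the choice could be made after the scores are seen.

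Satisfaction has a related but separate problem. Its single time point means that nobody who leaves before 3 months has a score, and a disappointed subject may be less likely to come back. At stake is whether the two subject-reported endpoints describe everyone treated or only those who stayed.

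**Working it through.** There is no document figure to reproduce: the plan gives a target of at least 70 completers, but no drop-out rate, score distribution or standard deviation. The check is first a reading of the rules, then an illustration on assumed inputs.

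**Step 1: scores due at each stopping point** (6.2, 8.1, Table 1, Appendix 1.0)

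| Subject leaves | Comfort scores due | Satisfaction scores | Covered by the non-evaluable rule in 7.2? |
|---|---|---|---|
| After treatment 1 | 1 | 0 | Yes |
| After treatment 2 | 2 | 0 | Yes |
| After treatment 3, before the 3-month visit | 3 | 0 | No, treatment was completed |
| Does not leave | 3 | 1 | No |

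Comfort scores exist in every row; for the first two rows the question is whether they are used. Satisfaction is absent in the first three rows. In the third row this follows from the single time point and the no-imputation rule, not from 7.2.

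**Step 2: 7.2 against 14.1.** Section 7.2 excludes the first two rows without naming an endpoint. Section 14.1 does not require completion of treatment. It would keep these subjects' comfort scores if comfort counts as a performance measurement, but that term is undefined. Comfort is not assigned to the safety set either, and that set is worded for Embrace procedures rather than Trim II.

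**Step 3: illustration for comfort.** Assumptions: 70 completers with a mean of 3 on the 0-10 scale; k stoppers, each with a score for the session summarised; a fraction f of stoppers score 8 and the rest score 3. For drop-out rate d, the number treated is N = 70/(1 − d), rounded up, and k = N − 70. Then

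mean over all treated = [70 × 3 + k(8f + 3(1 − f))]/N = 3 + 5fk/N.

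| d | N | k | f = 0 | f = 0.25 | f = 1 |
|---|---|---|---|---|---|
| 5% | 74 | 4 | 3.00 | 3 + 5/74 = 3.07 | 3 + 20/74 = 3.27 |
| 10% | 78 | 8 | 3.00 | 3 + 10/78 = 3.13 | 3 + 40/78 = 3.51 |
| 15% | 83 | 13 | 3.00 | 3 + 16.25/83 = 3.20 | 3 + 65/83 = 3.78 |
| 20% | 88 | 18 | 3.00 | 3 + 22.5/88 = 3.26 | 3 + 90/88 = 4.02 |

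A completers-only analysis reports 3.00 in every cell. The share who stop because of pain matters as much as the drop-out rate.

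**Step 4: illustration for satisfaction.** Assume 70 subjects answer and 70% of them are satisfied (49). The k others, whether they stopped or did not return, have unknown views. The share satisfied among all treated lies between 49/N (none satisfied) and (49 + k)/N (all satisfied).

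| N | Lowest | Highest |
|---|---|---|
| 74 | 49/74 = 66.2% | 53/74 = 71.6% |
| 78 | 49/78 = 62.8% | 57/78 = 73.1% |
| 83 | 49/83 = 59.0% | 62/83 = 74.7% |
| 88 | 49/88 = 55.7% | 67/88 = 76.1% |

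These are limits, not estimates. The documents do not say where in the range the truth would lie.

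**The case against.** The case against is substantial, and most of it stands.

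- A reader might infer that comfort has no usable score for subjects who stop. The documents do not support that: discomfort is rated straight after each session, so the score precedes the decision to leave.
- A reader might take 7.2 as settling the matter. It does not, because the section that defines the analysis sets, 14.1, does not require completion. The defect is an unresolved conflict, not a fixed exclusion.
- Pain that leads to stopping is not lost to the study. Section 6.1 has reactions assessed after each treatment, 9.2 lists pain, 9.4 requires all adverse events to be recorded for each subject, and the safety set needs only one use. This limits the harm. It does not repair the comfort endpoint, because a severity grade for an adverse event does not supply a comfort score.
- The switch described in section 4 pauses treatment, and intensity can be adjusted. Nothing says that discomfort makes people leave, and 7.2 allows withdrawal for any reason. A favourable bias is therefore a risk, not a demonstrated fact.
- It is tempting to say that replacement hides the loss because the completer count returns to 70. No section says that withdrawals or numbers enrolled will go unreported, and 11.1 asks for an explanation of all missing data.
- Neither endpoint has a success criterion, so no declared conclusion of the trial turns on them.

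What survives is that two sections give different populations for data already in hand, and the stricter one may remove unfavourable scores.

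**Conclusion.** The point holds as an unreconciled rule with a possible bias, at the level of a cheap improvement. Read literally, 7.2 discards comfort scores that 14.1 may or may not retain. If discomfort is one reason for stopping, the discarded scores would tend to be the worse ones and the summary would favour the device. Satisfaction describes only those who return, whether the others stopped treatment or finished it and did not come back.

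The size is unknown. Under the assumptions shown, with 10% stopping, the comfort mean moves from 3.0 to about 3.1 (a quarter of stoppers score 8) or about 3.5 (all do), and does not move if stoppers resemble completers. A reported 70% satisfied could correspond to anything from 62.8% to 73.1% of those treated. A reader might go further and conclude that the tolerability and satisfaction results are biased in the device's favour. The documents give no reasons for stopping and no scores, so they support only the possibility.

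**What to change.** 1. In 7.2, limit the non-evaluable rule so that it governs replacement only and does not remove data already collected.
2. In 14.1, state that therapy comfort is analysed in all subjects treated at least once, including those later replaced, and is reported by session with the denominator for each session. Add a matching line to the comfort endpoint in 6.2.
3. Report satisfaction as observed, with the number treated and the number answering beside it. Counting non-responders as not satisfied is at most an optional sensitivity analysis: it labels unrelated withdrawals as dissatisfied and departs from the no-imputation rule in 14.1.

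The cost is a few sentences and one table. No new data are needed, since comfort is already collected at every session. The downside for the sponsor is that the comfort figures may become slightly less favourable.

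Separately, 6.2 describes a 0-10 pain scale, while Table 1 points to the Appendix 5.0 comfort questionnaire, which runs from +2 to −2. The two must be reconciled before any comfort score is summarised.
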